6.3 Study procedures

The study will be executed in centres with sufficient experience in executing laparoscopic niche resections (> 30 previous laparoscopic niche resections).

6.3.1 Methods and measurements

Before randomisation, in every patient a transvaginal ultrasound (TVU) and a saline infusion sonography (SIS) or gel infusion sonography (GIS) is performed to assess the niche. Both procedures are subject of normal diagnostic tools for defining the origin of their gynaecological complaints. During ultrasound (SIS or GIS) the niche will be measured in the sagittal plane where the largest niche is visible (maximum depth, thinnest residual myometrium). Depth, width, largest diameter, residual myometrium and the shape of the main niche will be registered in the sagittal and transversal plane. In case of a lateral branch of the niche depth, width and the residual myometrium of the branch will be additionally registered. (see appendix A, figure numbers 1-4) Besides measurements of the niche, other features such as position of the uterus, vascular pattern and eventual fibroids or adenomyosis, intracavitary and/or niche fluid accumulations, abnormalities at the fallopian tubes and/or ovaries are registered.

For inclusion in the study the main niche needs to have a depth of > 50% of the total myometrium thickness at the anterior wall and a residual myometrium of less than 3mm in one of the ultrasound planes using sonohysterography.

6.3.2 Method of inclusion and registration of baseline characteristics and surgical outcomes

CRF's are attached.

6.3.3 Registration of patient reported outcomes

Questions on fertility, received fertility therapies, time to conceive and pregnancy outcomes of following pregnancies will be registered. All other outcomes will be collected by digital questionnaires and digital validated menstrual score card (23) in both groups.

6.3.4 Niche evaluation during subsequent pregnancies

In both groups, a TVU will be repeated after 3 months. Patients willing to conceive will be followed to evaluate the course of their eventual pregnancy and its outcome. During their pregnancy ultrasounds at 12, 20 and 30 weeks will be made during regular check-ups evaluate the appearance and thickness of the residual myometrium. In order to standardize measurements, an e-learning program needs to be completed by the sonographers before participation to the study.

6.3.5 Cost-effectiveness and cost-utility analysis

Both a cost-effectiveness and cost-utility analysis will be performed.

6.3.6 Future research

Patients will be asked for consent to store one blood sample for future research e.g. on factors influencing wound healing.

7. STATISTICAL ANALYSIS

Interim analysis will not be performed because of the long term follow-up. Total follow-up include 2 year after randomisation.

Power Calculation. Assuming 40% pregnancies in the intervention group, 20% pregnancies in the control group, a significance level of 0.05 and a power of 0.80, we need 82 women in each group. Because we expect a drop-out rate of about 15%, we will include 100 subjects in each group.

8. ETHICAL CONSIDERATIONS

8.1 Regulation statement

The study will be conducted according to Good Clinical Practice (GCP), the principles of the Declaration of Helsinki (The International Response to Helsinki VI – The WMA's Declaration of Helsinki on Ethical Principles for Medical Research Involving Human Subjects, as adopted by the WMA General Assembly, New Delhi, India, October 2009) and in accordance with the Medical Research Involving Human Subjects Act (WMO) and other guidelines, regulations and acts.

8.2 Recruitment and consent

All patients with the presence of a large niche after CS and secondary unexplained subfertility or failed IVF or problems during their fertility therapy, will be informed about the clinical trial by the supervising gynecologist or by the attending resident. The patient will also obtain written information about the study from the gynecologist or resident. In case of participation, the informed consent form should be signed first by the patient and then by the gynecologist or resident prior to randomization.

8.3 Objection by minors or incapacitated subjects

Not applicable

8.4 Benefits and risks assessment, group relatedness

Risks and burden are linked to the protocol procedures of a laparoscopic niche resection. Procedures in the intervention are carried out by medically qualified personnel. A laparoscopic niche resection is a safe technique with a low complication rate reported (Vervoort et al. submitted). The study will only be executed in centres with sufficient experience in executing laparoscopic niche resections (> 30 previous laparoscopic niche resections). Participation is expected to be beneficial for patients allocated to the intervention group on reproductive outcomes. However this theory needs to be proven or rejected in the current study. A relatively disadvantage is that patients included in the study need to postpone the activities to become pregnant for a period of 6 months.

8.5 Compensation for injury

The sponsor/investigator has liability insurance, which is in accordance with article 7 of the WMO. The sponsor (also) has insurance, which is in accordance with the legal requirements in the Netherlands (Article 7 WMO). This insurance provides cover for damage to research subjects through injury or death caused by the study. In VUmc the insurance is taken out at Onderlinge Waarborgmaatschappij Centramed b.a., [name]. Both insurer and insurance meet the decision of requirements imposed on mandatory insurance for medical science with humans (Staatsblad 2003, 266). Patients included in this study will be informed about the insurance.

1. € 450.000,-- (i.e. four hundred and fifty thousand Euro) for death or injury for each subject who participates in the research;

2. € 3.500.000,-- (i.e. three million five hundred thousand Euro) for death or injury for all subjects who participate in the research;

The insurance applies to the damage that becomes apparent during the study or within 4 years after the end of the study.

8.6 Incentives

There are no incentives for subjects participating in this study.

9. SAFETY REPORTING

9.1 Section 10 WMO event

In accordance to section 10, subsection 1, of the WMO, the investigator will inform the subjects and the reviewing accredited METC if anything occurs, on the basis of which it appears that the disadvantages of participation may be significantly greater than was foreseen in the research proposal. The study will be suspended pending further review by the accredited METC, except insofar as suspension would jeopardise the subjects' health. The investigator will take care that all subjects are kept informed.

9.2 Adverse and serious adverse events

All adverse events reported spontaneously by the subject or observed by the investigator or his staff will be recorded. A serious adverse event is an undesirable medical occurrence or effect on a subject, which not necessary has a causal relation with the treatment, and

- causes death and/or;
- is life threatening and/or;
- requires hospitalisation or prolongation of existing in patients' hospitalisation and/or;
- results in persistent or significant disability, incapacity or inability to work and/or;
- causes a congenital anomaly or birth defect.

All SAEs will be reported to the accredited METC that approved the protocol, according to the requirements of that METC.

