Study population: Women (>18 years) with the presence of a large niche and secondary unexplained subfertility, failed IVF, or with problems during their fertility therapy, such as intrauterine accumulation of fluid and/ or difficulties during the introduction of the ET of IU catheter will be included.

Main study outcomes: *Primary outcome:* time to ongoing pregnancy, defined as a intrauterine pregnancy with a fetal heartrate at 12 weeks gestation. *Secondary outcomes:* Fertility and pregnancy outcomes, satisfaction and quality of life, surgical outcomes (intervention group), additional interventions, niche characteristics.

Economic evaluation: direct and indirect costs will be executed from a social perspective.

Measurements: will be performed at baseline, 3, 6, 12 and 24 months after randomisation (control) or surgery (intervention) using digital questionnaires. Niche features will be measured by sonohysterography (SIS/GIS) at baseline and at 3 months after randomisation (control group) or after surgery (intervention group) . Patients are motivated for measurement of the lower uterine segment (LUS) at 12, 20 weeks and at 30 weeks of gestation during regular pregnancy check-ups. Prognostic dissimilarities will be registered, like duration of subfertility and previous therapies. Medical consumption and medication use will be registered in a diary.

Sample size calculation: Assuming 40% pregnancies in the intervention group, 20% pregnancies in the control group, a significance level of 0.05 and a power of 0.80, we need 82 women in each group. Because we expect a drop-out rate of about 15%, we will include 100 subjects in each group. Primary outcome is time to an ongoing pregnancy.

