5. TREATMENT OF SUBJECTS

Investigational product/treatment

In this trial outcomes of laparoscopic niche resection will be compared to expective management (usual care).

Intervention group

In the therapy group fertility therapies will be allowed from 6 month onwards after laparoscopic niche resection, the uterine scar needs to heal before a pregnancy is allowed.

The patients allocated for laparoscopic niche resection will undergo a planned procedure under general anaesthesia in lithotomic position. Donnez et al. first describe the laparoscopic niche resection in 2008 (19). The niche resection is continuously guided by hysteroscopy. Strong adhesions are often seen between the niche/uterus and the bladder or the niche/uterus and the abdominal wall. Adhesions are lysed and the bladder is dissected from the anterior wall of the uterus and the niche. Due to the thin myometrium at the site of the niche, the niche can be illuminated with the hysteroscopic light and can be visualised laparoscopically. The niche and related fibrotic tissue is resected. The uterotomy is closed using at least four sliding knots that include the entire uterine wall including the endometrium. One inverted suture is placed across the closed wound to strengthen the wound. In case the uterus is (extreme) retroverse flexed, the round ligaments are shortened using 2 continuous running sutures (2.0 multifilament) (38). The anatomic result of niche closure is evaluated by hysteroscopy at the end of the procedure.

Control group/ expectant group

The control group will not receive any additional surgical intervention during the first twelve months. Patients are allowed to conceive immediately and if needed fertility therapies are allowed, indication for the fertility therapy will be based on the local protocol.

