6. METHODS

6.1 Study parameters/ outcome

6.1.1 Primary outcome:

Time to ongoing pregnancy, defined as a intrauterine pregnancy with a fetal heartrate at 12 weeks gestation.

6.1.2 Secondary outcomes:

Fertility and pregnancy outcomes:

- time to conceive
- number of (vital) pregnancies
- number of take home babies
- number of miscarriages
- number of patients with term delivery
- complications during pregnancy
- mode of delivery
- complications during the delivery

Satisfaction and QOL

- satisfaction (Lickert scale)
- Quality of life (SF36)
- EuroQol SD5

Gynecological symptoms:

- pain during menstruation (VRS)
- abdominal pain on non-menstruating days (VRS)
- urinary symptoms (shortlist of SFFI)
- reduction of postmenstrual spotting days

Surgical outcomes (intervention group):

- surgery time
- blood loss during surgery
- perioperative complications (major and minor).

Additional interventions:

- hormonal interventions to treat gynecological symptoms

- additional surgical interventions
- applied fertility therapies.

Niche characteristics:

- immediately after surgery using hysteroscopy

Niche characteristics 3 months after randomization:

- residual niche (size, volume)
- residual myometrium (RM)
- intra-uterine fluid collection
- angle between endometrial lining of the endocervix and corpus
- residual myometrium or thickness LUS during subsequent pregnancy (at 12, 20 and 30 weeks).

6.1.3 Other study parameters:

Baseline parameters: age, body mass index, ethnic background, religion, gestational age, previous vaginal delivery, maternal disease, planned or emergency section, cervical dilatation, birth weight, placental localisation, multiple pregnancy and postpartum complications (infection, hospital readmission) will be registered.

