6.2 Randomisation, blinding and treatment allocation

The patients will be asked by their gynaecologist (at the local centre) to participate in the trial. Patients will be randomly allocated to laparoscopic niche resection or expectant management for 12 months. Eligible patients will be informed about the aims, methods, design, benefits and possible disadvantages of the laparoscopic niche resection due to informed consent. The patient will be included in the study after signing informed consent. Then the randomisation will be performed centrally using a permuted block-design, stratified for recruiting centre.

Given the nature of the therapy, blinding is not possible.

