9.4 Data Safety Monitoring Board (DSMB)

Given the previous positive outcomes of the cohort study with a low complication rate we consider that a DSMB is not necessary. We also do not plan to execute an interim analyses.

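### Adverse events are captured passively and not linked to the existing questionnaires or diary, so a between-arm comparison, mainly of non-serious events, is open to ascertainment bias

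*Protocol*

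**What the plan says.** Section 9.2 of the protocol states the capture rule, in the same words for both arms: "All adverse events reported spontaneously by the subject or observed by the investigator or his staff will be recorded". It then defines serious events by their outcome, whatever the cause, and sends them to the ethics committee.

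The setting in which the rule operates:

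- **Blinding** (section 6.2): "Given the nature of the therapy, blinding is not possible".
- **Surgery** (section 5): the intervention arm has a planned laparoscopy under general anaesthesia. For the other arm, "The control group will not receive any additional surgical intervention during the first twelve months".
- **Follow-up** (Summary, Measurements): assessments "will be performed at baseline, 3, 6, 12 and 24 months after randomisation (control) or surgery (intervention) using digital questionnaires". A diary of care and medicines used is also kept.
- **Other outcomes** (section 6.3.3): "All other outcomes will be collected by digital questionnaires and digital validated menstrual score card (23) in both groups".
- **Oversight** (section 9.4): "Given the previous positive outcomes of the cohort study with a low complication rate we consider that a DSMB is not necessary". No interim analysis is planned.

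**The concern.** A rule based on volunteering and observation captures more when a woman is seen more often, and when she or her clinician expects a harm. Here both are tied to allocation. The operated arm passes through theatre and perioperative care, and everyone knows who had surgery. The same wording can therefore yield different completeness in the two arms.

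The rule also says nothing about asking for events that another hospital or a general practitioner has treated. Such events may be lost in either arm.

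Two things are at stake. The Introduction says that controlled studies of laparoscopic niche repair are lacking, so this trial is a chance to obtain controlled data on harms. And with no DSMB and no interim analysis, the duty in section 9.1 to act if the disadvantages prove greater than foreseen depends on events reaching the investigator.

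**Working it through.** The protocol gives no adverse event rate, capture rate or safety test, so it has no figure of its own to reproduce. The check has two parts.

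**1. What is collected, and does it feed the adverse event record?**

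| Harm | Where collected | Arms | Link to adverse event record stated? |
|---|---|---|---|
| Perioperative complications | 6.1.2, surgical outcomes | Intervention only | No |
| Pregnancy and delivery complications, miscarriages | 6.1.2 | Not restricted | No |
| Pain, urinary symptoms | 6.1.2 | Not restricted | No |
| Additional surgical or hormonal interventions | 6.1.2 | Not restricted | No |
| Use of care (admissions and emergency visits would be forms of it) | Summary, diary | Not restricted | No |
| Infection or another complication after randomisation, outside these lists | 9.2 only | Both, passively | Not applicable |

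So many harms are gathered in a structured way, but section 9.2 draws on none of these sources. Harms outside the lists rest on the passive rule alone.

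**2. Scheduled or expected contact with staff**

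- *Intervention:* the operation, a 3-month scan, scans at 12, 20 and 30 weeks of any pregnancy, and fertility care from 6 months after surgery.
- *Control:* no operation for 12 months, a 3-month scan, the same pregnancy scans, and fertility care from the start where needed.

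The clear asymmetry is the perioperative period. Outside it, contact could be similar, or even greater early on for controls who have fertility treatment. The questionnaires also run from surgery in one arm and from randomisation in the other, so the observation windows differ.

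**3. What a capture gap would do (assumed inputs)**

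Let the true risk p be equal in both arms, with capture c1 (surgery) and c0 (control).

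- Recorded risk = p × c
- Risk ratio = c1 / c0, because p cancels
- Risk difference = p × (c1 − c0)

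With p from 10% to 30%:

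| Capture, surgery vs control | Risk ratio | Risk difference |
|---|---|---|
| 90% vs 90% | 0.90 / 0.90 = 1.00 | 0 |
| 90% vs 70% | 0.90 / 0.70 = 1.29 | 2 to 6 points |
| 90% vs 50% | 0.90 / 0.50 = 1.80 | 4 to 12 points |
| 70% vs 90% (reversed) | 0.70 / 0.90 = 0.78 | −2 to −6 points |

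Example at p = 20% with 90% vs 50%: 0.20 × 0.90 = 18% and 0.20 × 0.50 = 10%. That is 11.7 against 6.5 women of 65 per arm (130 in total in section 4.3, allocated 1:1), or 18 against 10 of 100 per arm (the size in section 7).

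Equal but incomplete capture is a separate problem. At 50% in both arms the ratio stays 1.00, but a true 20% is reported as 10% in each. This is how late events treated elsewhere would be understated.

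**The case against.** The strongest reply is that the passive rule is only part of the picture. Section 6.1.2 lists several harms without restriction to one arm, including "complications during pregnancy". Section 6.3.3 collects outcomes by questionnaire in both groups, the diary registers use of care, and pregnancies are followed with scans. The rule in 9.2 is identical for both arms. No between-arm test or table of adverse events is specified. Perioperative complications can occur only with surgery, so recording them in one arm is not bias. The case report forms mentioned in section 6.3.2 are not shown and may contain prompts.

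Most of this stands, and it rules out stronger readings that a reader might infer:

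- *That harms are captured unequally and the safety comparison is biased.* The documents show a mechanism, not a measured gap. With equal capture there is no bias in the ratio.
- *That these reports are the only safety data.* The listed outcomes contradict this.
- *That pregnancy complications handled elsewhere would be lost.* Sections 6.1.2, 6.3.3 and 6.3.4 plan to collect the course, complications and outcome of pregnancies.
- *That the 3-month scan is the only contact for controls.* Pregnancy scans and fertility care add contacts.

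The reply does not remove the gap in section 9.2 itself. How adverse events are elicited is a matter of data collection, and 9.2 settles it. The heading of section 6.3.2 covers baseline characteristics and surgical outcomes, not adverse events. No stated step carries a questionnaire or diary answer into an adverse event form.

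**Conclusion.** The point holds in a limited form. Section 9.2 fixes passive capture in an open-label trial in which one arm has surgery and perioperative contact, and it leaves structured sources already in place unlinked to the adverse event record. Any comparison of adverse events between arms, mainly of non-serious ones, would be open to ascertainment bias. The likely direction is more recorded events around surgery, although contact outside that period could run the other way. Late events treated elsewhere may be under-recorded in both arms.

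The size is unknown. The risk ratios of 1.00 to 1.80 rest entirely on assumed capture rates and show only that the effect could range from none to material. Events that meet the serious criteria, such as death or hospitalisation, depend less on prompting. The primary outcome, time to ongoing pregnancy, is not affected. This is an inexpensive improvement to harm reporting and does not threaten the trial's main conclusion.

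**What to change.** Amend section 9.2 as follows:

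1. Add the same short closed harm questions to the existing 3, 6, 12 and 24 month questionnaires in both arms: for example, any hospital admission, emergency visit, infection or other complication since the last form. Ask for the date of each event, because the questionnaires start from different time points in the two arms.
2. State that a positive answer to these questions, to the listed outcome items or in the medical-consumption diary prompts the site to complete an AE/SAE form.
3. Keep spontaneous and staff-observed reports, and tabulate them separately from elicited ones, so that a reader can see how far a difference depends on the route of capture.

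The cost is a few items on questionnaires already sent, plus site follow-up of positive answers. The downside is that more minor events will have to be recorded and processed.

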9.3 Follow up of adverse events

All adverse events will be followed until they have abated, or until a stable situation has been reached. Depending on the event, follow up may require additional tests or medical procedures as indicated, and/or referral to the general physician or a medical specialist.

9.4 Data Safety Monitoring Board (DSMB)

Given the previous positive outcomes of the cohort study with a low complication rate we consider that a DSMB is not necessary. We also do not plan to execute an interim analyses.

10. ADMINISTRATIVE ASPECTS

10.1 Handling and storage of data and documents

Subject numbers will be assigned sequentially to subjects enrolled in the study. All data, collected in this research protocol will be treated confidential and will be identified with the subject number not with subjects name, patient number or address. Next to the case report file, used in the study, a regular clinical patient file will be kept. Members of the Medical Ethical committee are allowed to inspect the quality of accomplished research.

10.2 Amendments

A 'substantial amendment' is defined as an amendment to the terms of the METc application, or to the protocol or any other supporting documentation, that is likely to affect to a significant degree the:

- Safety or physical or mental integrity of the subjects of the trial;
- Scientific value of the trial;
- Conduct or management of the trial; or
- Quality or safety of any intervention used in the trial.

All substantial amendments will be notified to the METc and to the competent authority.

10.3 End of study report

All the study data will be combined at the end of the inclusion period. The investigator will notify the accredited METc and the competent authority at the end of the study within a period of 90 days. The end of the study is defined as the last patient's contact. In case the study is ended prematurely, the investigator will notify the accredited METc and the competent authority within 15 days, including the reasons for the premature termination. Within one year after the end of the study, the investigator will submit a final study report with the results of the study, including any publications/abstracts of the study, to the accredited METc and the Competent Authority.

